7.3.2. Bone Biomarkers

Bone biomarkers include serum CTX, P1NP, and PTH.

Baseline, postbaseline, change from baseline, and percentage change from baseline in bone biomarkers will be summarized by treatment group and visit using descriptive statistics for subjects in the Safety Analysis Set from baseline to Week 96. Percentage change from baseline will be compared between the 2 treatment groups using the Wilcoxon rank sum test.

Open-label baseline, open-label postbaseline, change from open-label baseline, and percentage change from open-label baseline in bone biomarkers will be summarized by treatment group and visit using descriptive statistics for subjects in the Open-Label Safety Analysis Set from open-label baseline to Week 96. No statistical comparisons will be performed.

Median (Q1, Q3) percentage change from the baseline to Week 96 in each bone biomarker over time will be plotted by treatment group for subjects in the Safety Analysis Set. This will be repeated using subjects in the Open-Label Safety Analysis Set from open-label baseline to Week 96.

7.3.3. Fracture Events

The PTs for fracture events were defined based on HLGT of Fractures from the most current version of MedDRA at the time of the analysis (see Appendix 3). The number and percentage of subjects in the Open-Label Safety Analysis Set who experienced fracture events will be summarized by treatment group for the open-label phase. A data listing of fracture events will be provided.

7.3.4. Assessment of Fracture Probability

Fracture probabilities will be assessed using FRAX, a computer based algorithm developed by the World Health Organization (WHO; http://www.shef.ac.uk/FRAX).

The FRAX algorithm is based on individual patient models that integrate the risks associated with clinical risk factors as well as BMD at the femoral neck. The algorithm provides both the 10-year probability of hip fracture and the 10-year probability of a major osteoporotic fracture (clinical spine, forearm, hip, or shoulder fracture).

The FRAX model is constructed from real data in population-based cohorts around the world that have a limited age range. For an age below 40 or above 90 years, the tool will calculate the probability of fracture at the age of 40 or 90 years, respectively. Due to the age limitation, 2 sets of analyses of fracture probabilities will be performed.

In the first set of analysis, summaries of baseline and change from baseline to Week 96 in the 10-year probabilities of hip fracture, as well as major osteoporotic fracture, will be presented by treatment group and visit for subjects in the Safety Analysis Set aged between 40 and 90 years. Change from baseline in the 10-year fracture probabilities at each analysis visit will be compared between the 2 treatment groups using ANOVA, which includes treatment as a fixed effect.

In the second set of analysis, the above-specified analysis will be performed to include all subjects, where subjects in the Safety Analysis Set with an age below 40 or above 90 years will be treated as having an age of 40 or 90 years, respectively, in computing their fracture probabilities.

The analyses described above will be repeated for subjects in the Open-Label Safety Analysis Set from open-label baseline to Week 96, using open-label baseline in place of baseline, and no statistical comparisons will be performed.

Only data listings of fracture risk assessment questionnaire and FRAX fracture probabilities will be provided.

7.3.5. Bone Events

The PTs for bone events were defined based a search for bone disorder related adverse events reviewed by PVE using the most current version of MedDRA at the time of the analysis (see Appendix 2). The number and percentage of subjects in the Open-Label Safety Analysis Set who

experienced treatment-emergent bone events will be summarized by treatment group for the open-label phase. A data listing of bone events will be provided.

7.4. Renal Safety Analyses

7.4.1. Confirmed Renal Abnormalities

Confirmed renal abnormalities are defined as follows:

- Confirmed increase from open-label baseline in creatinine of at least 0.5 mg/dL or
- Confirmed creatinine clearance CLcr by CG below 50 mL/min or
- Confirmed phosphorous < 2 mg/dL

Confirmed renal abnormalities are defined as renal abnormalities at 2 consecutive open-label postbaseline visits. Treatment-emergent confirmed renal abnormalities during the open-label phase will be summarized, where open-label baseline will be defined as the last available record on or prior to Open-Label Study Day 1. All confirmed renal abnormalities including those that occur during the open-label phase will be listed.

7.4.2. Serum Creatinine

For the renal safety analyses, observed creatinine values will be used.

For subjects in the Safety Analysis Set, the baseline and change from baseline in serum creatinine during the entire study period will be summarized using descriptive statistics. The baseline serum creatinine and change from baseline in serum creatinine will be compared between the 2 treatment groups using the two-sided Wilcoxon rank sum test.

For subjects in the Open-Label Safety Analysis Set, the open-label baseline and change from open-label baseline in serum creatinine during the open-label phase will be summarized using descriptive statistics. No statistical comparisons will be performed.

Median (Q1, Q3) and mean (95% CIs) of change from baseline to Week 96 in serum creatinine over time will be plotted by treatment group for subjects in the Safety Analysis Set. This will be repeated using subjects in the Open-Label Safety Analysis Set from open-label baseline to Week 96.

7.4.3. Estimated Glomerular Filtration Rate

Estimated glomerular filtration rate will be summarized for subjects in the Safety Analysis Set from baseline to Week 96.

The following formulae will be used to calculate eGFR:

• CG based:

```
eGFRcg (mL/min) [(140 age (yrs)) \times weight (kg) \times (0.85 if female)] / (SCr (mg/dL) \times 72), where weight is actual total body mass in kilograms, and SCr is serum creatinine.
```

• CKD-EPI Creatinine based:

```
eGFRCKD EPI, creatinine (mL/min/1.73 m^2) 141 \times \min(SCr/\kappa, 1)^{\alpha} \times \max(SCr/\kappa, 1)^{1.209} \times 0.993^{age} \times 1.018 (if female) \times 1.159 (if black),
```

where κ is 0.7 for females and 0.9 for males, α is 0.329 for females and 0.411 for males, min indicates the minimum of SCr/ κ or 1, and max indicates the maximum of SCr/ κ or 1 {Levey 2009}.

• CKD-EPI Cystatin C based:

```
eGFRCKD EPI, cysC (mL/min/1.73 m^2) 133 \times min(SCys/0.8, 1)^{0.499} \times max(SCys/0.8, 1)^{1.328} \times 0.996^{age} [\times 0.932 \text{ if female}],
```

where SCys is serum cystatin C.

P-values for the baseline, the change from baseline in eGFR $_{CG}$ and eGFR $_{CKD}$ $_{EPI,\ creatinine}$ will be estimated from the 2-sided Wilcoxon rank sum test to compare the 2 treatment groups. For eGFR $_{CKD}$ $_{EPI,\ cysC}$, only the baseline value will be summarized as the postbaseline tests were only performed as reflex tests.

The number and proportion of subjects with decrease from baseline of $\geq 25\%$ and $\geq 50\%$ in eGFRcg and eGFR ckd EPI, creatinine will be summarized by treatment groups for subjects in the Safety Analysis Set from baseline to Week 96. Statistical comparisons of the subject incidence rates between the 2 treatment groups during the entire study period will be performed using Fisher's exact test.

The number and proportion of subjects in each stage of chronic kidney disease (CKD) will be summarized by baseline stages of CKD at Weeks 12, 24, 36, 48, 60, 72, and 96 for the entire study treatment period based on subjects in the Safety Analysis Set. The distribution of the stages of CKD at these visits will be compared between the 2 treatment groups adjusting for entire study treatment period using rank ANCOVA {LaVange 2008}.

The stages of CKD are defined as follows:

- Stage 1: eGFRcg≥ 90 mL/min
- Stage 2: eGFRcg \geq 60 and \leq 90 mL/min
- Stage 3: eGFRcg \geq 30 and \leq 60 mL/min
- Stage 4: eGFRcg < 30 mL/min

The summaries described above will be repeated for subjects in the Open-Label Safety Analysis Set from open-label baseline to Week 96, using open-label baseline in place of baseline, and no statistical comparisons will be performed.

Median (Q1, Q3) change from baseline in eGFR by CG and by CKD-EPI Creatinine over time will be plotted by treatment group for subjects in the Safety Analysis Set from baseline to Week 96. This will be repeated for subjects in the Open-Label Safety Analysis Set from open-label baseline to Week 96.

7.4.4. Treatment-Emergent Proteinuria (Dipstick)

Treatment-emergent proteinuria by urinalysis (dipstick) will be summarized by treatment group for the subjects in the Open-Label Safety Analysis Set during the open-label phase. A listing of subjects with treatment-emergent proteinuria will be provided.

7.4.5. Urine Creatinine, Urine RBP to Creatinine Ratio and Beta-2-Microglobulin to Creatinine Ratio

Baseline, postbaseline, change from baseline and percentage change from baseline in urine creatinine, urine RBP to creatinine ratio, and beta-2-microglobulin to creatinine ratio will be summarized by treatment group and visit using descriptive statistics during the double-blind and open-label phase. The difference in percentage change from baseline in these ratios between the 2 treatment groups will be tested using the Wilcoxon rank sum test only for the entire study period summary.

The summary described above will be repeated for subjects in the Open-Label Safety Analysis Set from open-label baseline to Week 96, using open-label baseline in place of baseline, and no statistical comparisons will be performed.

Median (Q1, Q3) percentage change from the baseline in the urine RBP to creatinine ratio, and beta-2-microglobulin to creatinine ratio over time will be plotted by treatment group for subjects in the Safety Analysis Set from baseline to Week 96. This will be repeated for subjects in the Open-Label Safety Analysis Set from open-label baseline to Week 96.

7.4.6. Proteinuria by Quantitative Assessment

Baseline, postbaseline, changes from baseline, and percentage change from baseline in UPCR and UACR will be summarized by treatment group and visit using descriptive statistics, for subjects in the Safety Analysis Set from baseline to Week 96. Percentage change from baseline will be compared between the 2 treatment groups using the Wilcoxon rank sum test only for the entire study period summary.

The number and proportion of subjects with UPCR \leq 200 mg/g versus > 200 mg/g will be summarized by baseline category for each postbaseline visit during the entire study treatment period {KDIGO Guideline Development Staff 2013}.

The number and proportion of subjects with UACR $< 30 \text{ mg/g versus} \ge 30 \text{ mg/g will be}$ summarized by baseline category for each postbaseline visit during the entire study treatment period {KDIGO Guideline Development Staff 2013}.

The distribution of the UPCR and UACR categories during the entire study period will be compared between the 2 treatment groups adjusting for baseline categories using rank ANCOVA {LaVange 2008}, respectively.

The summaries described above will be repeated for subjects in the Open-Label Safety Analysis Set from open-label baseline to Week 96, using open-label baseline in place of baseline, and no statistical comparisons will be performed.

Median (Q1, Q3) percentage change from baseline in the 2 ratios over time will be plotted by treatment group for subjects in the Safety Analysis Set from baseline to Week 96. This will be repeated for subjects in the Open-Label Safety Analysis Set from open-label baseline to Week 96.

7.4.7. Other Renal Biomarkers

Other renal biomarkers include TmP/GFR and FEPO₄.

TmP/GFR based on serum creatinine {Barth 2000} will be calculated as follows:

$$TmP/GFR = TRP \times SPO_4$$
 if $TRP \le 0.86$
 $TmP/GFR = 0.3 \times TRP/[1 \quad (0.8 \times TRP)] \times SPO_4$ if $TRP > 0.86$

where TRP (tubular reabsoprtion of phosphate) is calculated by:

$$TRP \quad 1 \quad \frac{UPO_4}{SPO_4} \times \frac{SCr}{UCr}$$

where SCr is serum creatinine concentration (mg/dL), UPO₄ is urine phosphate concentration (mg/dL), SPO₄ is serum phosphate concentration, and UCr is urine creatinine concentration (mg/dL).

Urine FEPO⁴ will be calculated as follows:

FEPO₄ (%)
$$(SCr \times UPO_4) / (SPO_4 \times UCr) \times 100$$
 (%)

The baseline, postbaseline, and change from baseline in TmP/GFR and FEPO₄ will be summarized by treatment group and visit using descriptive statistics during the double-blind and open-label phase using the subjects in the Safety Analysis Set. Baseline and change from baseline will be compared between the 2 treatment groups using the Wilcoxon rank sum test only for the entire study period.

The summaries described above will be repeated for subjects in the Open-Label Safety Analysis Set from open-label baseline to Week 96, using open-label baseline in place of baseline, and no statistical comparisons will be performed.

Median (Q1, Q3) change from the baseline in TmP/GFR and FEPO₄ over time will be plotted by treatment group for subjects in the Safety Analysis Set from baseline to Week 96. This will be repeated for subjects in the Open-Label Safety Analysis Set from open-label baseline to Week 96.

7.5. Child-Pugh-Turcotte Score

The Child-Pugh-Turcotte (CPT) score is calculated as: the sum of the scores related to the 5 items in the table below (if any of the components are missing, the score is not calculated):

Measure	1 point	2 points	3 points
Total Bilirubin (mg/dL)	< 2	2 - 3	> 3
Serum Albumin (g/dL)	> 3.5	2.8 - 3.5	< 2.8
INR	< 1.7	1.7 - 2.3	> 2.3
Ascites	None	Slight/Moderate (medically controlled)	Severe (medically uncontrolled)
Hepatic Encephalopathy	None	Slight/Moderate (medically controlled)	Severe (medically uncontrolled)

For summary purposes, the score will be further classified into classes: Class A (5-6 points), Class B (7-9 points), and Class C (10-15 points). The number and proportion of subjects in each class of CPT score will be summarized in a shift table with baseline, Week 48, and Week 96 CPT class based on subjects in the Safety Analysis Set during the entire study treatment period. The distribution of the CPT class at these visits will be compared between the 2 treatment groups adjusting for baseline class using rank ANCOVA {LaVange 2008}.

The summaries described above will be repeated for subjects in the Open-Label Safety Analysis Set from open-label baseline to Week 96, using open-label baseline in place of baseline, and no statistical comparisons will be performed.

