Table 1-11. GS-US-320-0108 and GS-US-320-0110: Treatment-Emergent Grade 3 or 4 Laboratory Abnormalities Reported for at Least 1% of Subjects in Either Treatment Group in the Overall TAF Phase 3 Safety Population (Safety Analysis Set)

	TAF 25 mg (N = 866)	TDF 300 mg (N = 432)
Maximum Postbaseline Toxicity Grade (N)	859	428
Grade 3	225 (26.2%)	96 (22.4%)
Grade 4	44 (5.1%)	30 (7.0%)
Chemistry		
Alanine Aminotransferase (N)	859	428
Grade 3	52 (6.1%)	27 (6.3%)
Grade 4	18 (2.1%)	13 (3.0%)
Amylase (N)	859	427
Grade 3	22 (2.6%)	9 (2.1%)
Aspartate Aminotransferase (N)	859	428
Grade 3	25 (2.9%)	18 (4.2%)
Grade 4	3 (0.3%)	5 (1.2%)
Creatine Kinase (N)	859	428
Grade 3	16 (1.9%)	7 (1.6%)
Grade 4	9 (1.0%)	6 (1.4%)
Fasting Glucose (Hyperglycemia) (N)	857	425
Grade 3	9 (1.1%)	0
Fasting LDL Cholesterol (N)	837	417
Grade 3	37 (4.4%)	1 (0.2%)
Nonfasting Glucose (Hyperglycemia) (N)	856	426
Grade 3	25 (2.9%)	7 (1.6%)
Urinalysis		
Occult Blood (N)	859	426
Grade 3	66 (7.7%)	30 (7.0%)
Urine Erythrocytes (N)	768	386
Grade 3	59 (7.7%)	35 (9.1%)
Urine Glucose (N)	859	426
Grade 3	41 (4.8%)	5 (1.2%)

Denominator for percentage (N) is the number of subjects in the safety analysis set with at least 1 postbaseline laboratory value for the test.

Subjects were counted once for the maximum postbaseline severity for each laboratory test. For urinalysis (ie, urine glucose, urine protein, and urine RBC), the highest grade is Grade 3.

For nonfasting glucose, the maximum postbaseline toxicity grades, instead of treatment-emergent abnormalities, were summarized, because nonfasting glucose test was not done at baseline.

Source: TAF Week 48 ISS, Table 20

Hepatic Laboratory Abnormalities

In Studies GS-US-320-0108 and GS-US-320-0110 the incidence of graded hepatic laboratory abnormalities through the Week 48 data cutoff date was generally lower for subjects in the TAF group compared with subjects in the TDF group, and included ALT increased

^{&#}x27;Hyper' means high and 'Hypo' means low.

(TAF 22.8%,196 subjects; TDF 30.4%, 130 subjects), AST increased (TAF 22.2%, 191 subjects; TDF 25.2%, 108 subjects), total bilirubin increased (TAF 12.7%, 109 subjects; TDF 10.0%, 43 subjects), gamma-glutamyltransferase (GGT) increased (TAF 7.5%, 64 subjects; TDF 10.0%, 43 subjects), alkaline phosphatase increased (TAF 2.2%, 19 subjects; TDF 5.4%, 23 subjects), and albumin decreased (TAF 0.9%, 8 subjects; TDF 1.9%, 8 subjects).

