4.3. Exclusion Criteria

Subjects who meet any of the following exclusion criteria are not to be enrolled in this study:

- 1) Pregnant women, women who are breastfeeding or who believe they may wish to become pregnant during the course of the study
- 2) Males and females of reproductive potential who are unwilling to use an "effective", protocol-specified method(s) of contraception during the study. For a list of protocol-specified Contraceptive methods, refer to Appendix 5.

- 3) Co-infection with HCV, HIV, or HDV
 - Subjects who are HCV positive, but have a documented negative HCV RNA, are eligible
- 4) Evidence of hepatocellular carcinoma (e.g. as evidenced by recent imaging)
- 5) Current evidence of, or recent (\leq 5 years) history of clinical hepatic decompensation (e.g., ascites, encephalopathy or variceal hemorrhage)
- 6) Abnormal hematological and biochemical parameters, including:
 - a) Hemoglobin < 10 g/dL
 - b) Absolute neutrophil count < 750/mm³
 - c) Platelets $\leq 50,000/\text{mm}^3$
 - d) AST or ALT $> 5 \times ULN$
 - e) Albumin < 3.0 mg/dL
 - f) INR $> 1.5 \times$ ULN (unless stable on anticoagulant regimen)
 - g) Total bilirubin $> 2.5 \times ULN$
- 7) Received solid organ or bone marrow transplant
- 8) Significant renal, cardiovascular, pulmonary, or neurological disease in the opinion of the investigator
- 9) Malignancy within 5 years prior to Screening, with the exception of specific cancers that are cured by surgical resection (e.g. basal cell skin cancer, etc.). Subjects under evaluation for possible malignancy are not eligible.
- 10) Currently receiving therapy with immunomodulators (e.g. corticosteroids), nephrotoxic agents, or agents capable of modifying renal excretion
- 11) Known hypersensitivity to study drugs, metabolites, or formulation excipients
- 12) Current alcohol or substance abuse judged by the investigator to potentially interfere with subject compliance
- 13) Any other clinical condition or prior therapy that, in the opinion of the Investigator, would make the subject unsuitable for the study or unable to comply with dosing requirements.
- 14) Use of investigational agents within 3 months of screening, unless allowed by the Sponsor
- 15) Use of any prohibited medications as described in Section 5.4. Subjects on prohibited medications who are otherwise eligible will need a wash out period of at least 30 days prior to the Baseline visit

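### SAP 7.5 compares the arms on Child-Pugh-Turcotte class only, so a worsening from 5 to 6 points cannot register; the score it already derives should be compared

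*SAP*

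**What the plan says.** SAP 7.5 sums five items (bilirubin, albumin, INR, ascites, encephalopathy) into a CPT score; "if any of the components are missing, the score is not calculated". The score is then grouped as "Class A (5-6 points), Class B (7-9 points), and Class C (10-15 points". The numbers in each class "will be summarized in a shift table with baseline, Week 48, and Week 96 CPT class", using the Safety Analysis Set. The between-arm comparison follows: "The distribution of the CPT class at these visits will be compared between the 2 treatment groups adjusting for baseline class using rank ANCOVA".

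The section plans no descriptive summary and no test of the score. It does not say what happens if all subjects fall in one class.

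Protocol 4.3 excludes current or recent (5 years or less) "history of clinical hepatic decompensation (e.g., ascites, encephalopathy or variceal hemorrhage". It also excludes low albumin (printed as "Albumin < 3.0 mg/dL"), bilirubin above 2.5 times the upper limit of normal (ULN), and INR above 1.5 times ULN unless the subject is stable on an anticoagulant. There is no Child-Pugh entry criterion, and Protocol 3.1 admits compensated cirrhosis. CPT is not among the endpoints in Protocol 8.1.2 to 8.1.4, nor in the testing sequence of Protocol 8.4.

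**The concern.** Class A covers both 5 and 6 points. A subject at 5 whose albumin falls to 3.5 g/dL, or whose bilirubin reaches 2 mg/dL, gains one point and stays in class A. In a population expected to sit almost entirely at 5 or 6, the commonest possible worsening is the one that the test cannot see.

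The SAP does not limit itself in this way elsewhere. It tests eGFR change as well as kidney disease stage (7.4.3), and percentage change in UPCR and UACR as well as their categories (7.4.6). FibroTest score is tested and its stage is shown as a shift table (6.2.2). For CPT only the coarse grouping is used, and the only reason given is summary purposes.

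CPT is the only planned between-arm test of a composite of liver synthetic and excretory function and decompensation. The risk is that a non-significant class test, or a missing p-value, is quoted as hepatic reassurance that it cannot give.

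**Working it through.** **1. Number of subjects.** Protocol 8.9 gives 230 per arm: 80% power, one-sided 0.025, 2.4% in both arms, margin 4%. Check: n = (1.960 + 0.842)² × 2 × 0.024 × 0.976 / 0.04² ≈ 230. The figure reproduces, and it fixes n for CPT. The documents state no power for the CPT test; two-sided 0.05 is assumed below.

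**2. Highest possible score at entry.** Albumin is read in g/dL for this calculation only, and ULNs of 1.0 to 1.2 are assumed for bilirubin (mg/dL) and INR.
- Ascites 1 and encephalopathy 1, since decompensation is excluded.
- Albumin 3.0 to 3.5 is allowed: 2 points.
- Bilirubin up to 2.5 to 3.0 mg/dL is allowed: 2 points.
- INR up to 1.5 to 1.8 is allowed: 1 or 2 points (2 from 1.7).

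Total: 1 + 1 + 2 + 2 + (1 or 2) = 7 or 8, which is class B. Class A at entry is therefore expected for nearly all, but not guaranteed.

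**3. Power on class.** If baseline class is constant and nobody is class C, the rank ANCOVA reduces to a comparison of two proportions. With m subjects in class B overall, a of them in one arm, and N = 460:

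X² = (a − m/2)² / [m(N − m) / (4(N − 1))].

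For 4 versus 0: (4 − 2)² / [4 × 456 / (4 × 459)] = 4.03, p = 0.045. For 3 versus 0, p = 0.083. So at least 4 versus 0 is needed. Exact binomial enumeration at assumed rates gives:

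| Class B/C, arm 1 vs arm 2 | Power |
|---|---|
| 0.5% vs 1% | 7% |
| 1% vs 2% | 13% |
| 0.5% vs 2% | 29% |
| 1% vs 4% | 56% |

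**4. No p-value.** If all 460 are class A at a visit, the variance is zero. The probability is (1 − p)^460: 40% at an overall rate p of 0.2%, 10% at 0.5%, and 1% at 1%.

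**5. Score against class on the same simulated subjects.** 230 per arm, 3,000 runs. Assumed baseline: 95% at 5 points, 4.8% at 6, 0.2% at 7. Assumed worsening: one point in 85% of those who worsen, two points in 15%. The score test adjusts for baseline score and the class test for baseline class.

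| Worsening, arm 1 vs arm 2 | Power on score | Power on class |
|---|---|---|
| 2% vs 5% | 41% | 7.5% |
| 2% vs 8% | 87% | 24% |
| 5% vs 12% | 76% | 17% |

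With a baseline mix of 92/7.5/0.5 the pairs are 39% and 10%, 85% and 26%, and 76% and 21%. With 2% worsening in both arms, the score test rejects in about 5% of runs, so the gain does not come from excess false positives.

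**6. The only proxy in the documents.** Protocol 1.2.3 reports "albumin decreased (TAF 0.9%, 8 subjects; TDF 1.9%, 8 subjects" in the two Phase 3 studies. Taking 0.9% and 1.9% as one-point worsening rates, with 207 per arm (90% of 230) and 2 to 5% at 6 points at baseline, simulated power is about 12% on the score and 0% on class. The class result follows largely from allowing only one-point moves. For 80% power on the score, n ≈ (1.960 + 0.842)² × (0.009 × 0.991 + 0.019 × 0.981) / 0.01² = 7.85 × 0.02756 / 0.0001, or about 2,160 per arm.

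**The case against.** A, B and C are the score's own classes, and reporting them is a defensible choice. If everyone stays in class A, the shift table shows that plainly and a missing p-value misleads nobody. Movement in albumin and bilirubin is not lost: SAP 7.2.1 summarises every laboratory test by arm and visit, and SAP 7.2.2.3 tabulates graded abnormalities by arm. At the only document-based rate the score test is weak too. That proxy is itself poor, being cumulative incidence in studies whose subjects were viremic at baseline. By Week 96 both arms will have been on TAF for 48 weeks, and the separate Week 48 SAP, which may have treated the score differently, is not among the documents. All of this stands and limits the consequence. None of it is a reason to derive the score and then leave it out of both the summary and the test.

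A reader might infer more than the documents support:
- **That the trial selects class A and excludes raised INR.** There is no Child-Pugh criterion, INR up to 1.5 times ULN is allowed (higher on stable anticoagulation), and 7 or 8 points at entry is possible.
- **That this is the only comparison of hepatic function.** SAP 6.2.2 tests ALT and FibroTest between arms.
- **That the class test has almost no power, or is often undefined.** Both depend on class B/C rates that the documents do not give. At 1% versus 4% power is 56%, and at an overall rate of 1% the chance of no p-value is 1%.

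**Conclusion.** The point holds as an improvement to a supportive safety analysis. The planned test cannot register a move from 5 to 6 points, and eligibility makes that the likeliest worsening. At small class B/C rates its power is low, and the plan has no rule for the case where all subjects share one class. In every scenario run, testing the score gave more power than testing the class.

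The direction of that gain is robust across the baseline mixes tried. Its size is not, because it rests on assumed baseline scores and worsening rates. CPT is outside type I error control and has no stated power, so nothing in the primary or key secondary conclusions is affected. Even with the score, power may be as low as about 12%, so a null result on either scale is not evidence of hepatic safety.

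**What to change.** In SAP 7.5:
- Compare the CPT score (5 to 15) between arms at Weeks 48 and 96 with the same rank ANCOVA, adjusted for baseline CPT score.
- Tabulate change in score (0, 1, 2 or more points) by arm.
- Keep the class shift table as descriptive only.
- State that no p-value is given when all subjects share one value, and that a non-significant result will not be presented as evidence of hepatic safety.

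The cost is a few lines of SAP text and one extra table. The score is already derived, and no new data are needed.
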